10.4 Quality of Life

Subject QOL will be evaluated using the EuroQOL 5 dimensions, 5 levels questionnaire (EQ-5D-5L), which measures 5 dimensions of health, including mobility, self-care, usual activities, pain/discomfort, anxiety, and general health and the European Organization for Research and Treatment of Cancer (EORTC) Quality of Life Questionnaire Core 30 (QLQ-C30), which are reliable and valid measures of QOL in cancer subjects. QOL will be evaluated at the times outlined in [Table 2](#). At each time point, the EQ-5D-5L is to be completed first, followed by the EORTC QLQ-C30.

The subject-reported assessments are for the purpose of exploring the subject's own perceptions about their symptoms and health-related QOL, and thus a proxy (ie, a caregiver or study personnel) should not complete the questionnaires. Additionally, the investigator must not influence the subject's assessments. Every effort should be made to maintain an unbiased assessment.

If a subject cannot complete the QOL instrument (questionnaire) because of illiteracy or other documented reason, the instrument should be omitted. Reasons for missing data will be documented and incorporated into the analysis as necessary.

EQ-5D-5L

The EQ-5D-5L is a standardized instrument for use as a measure of general health states preferences and provides a simple descriptive profile and index value for health status and measures 5 dimensions of health including mobility, self-care, usual activities, pain/discomfort, anxiety, and general health is measured via a vertical visual analog scale ([Rabin 2001](#)). Applicable to a wide range of health conditions and treatments, it provides a simple descriptive profile and a single index value for health status.

The subject-reported assessments are for the purpose of exploring the subject's own perceptions about their symptoms and health-related QOL and thus a proxy (ie, a caregiver or study personnel) should not complete the questionnaires. Additionally, the investigator must not

influence the subject's assessments. Every effort should be made to maintain an unbiased assessment.

At each scheduled assessment, the EQ-5D-5L should be administered before all other study procedures. If assessments were completed within the previous 7 days at a regularly scheduled visit, assessments do not need to be administered at the EOT visit.

Details of the algorithms that generate summary derived scores on each of the above health related QOL scales and the statistical approach for each will be provided in the Statistical Analysis Plan (SAP).

EORTC QLQ-C30

The EORTC QLQ-C30 was developed to assess the QOL of cancer subjects (Aaronson 1993). It has been translated and validated into 8 languages. It contains 5 functioning scales (physical, role, cognitive, emotional, and social), 3 symptom scales (fatigue, nausea, pain) and additional single symptom items. It is scored on a 4-point scale (1=not at all, 2=a little, 3= quite a bit, 4=very much). The EORTC QLQ-C30 instrument also contains 2 global scales that use 7-point scale scoring with anchors (1=very poor and 7=excellent).

10.5 Safety Assessments

The safety evaluation will be based on AE reporting, laboratory parameters, vital signs, physical examinations, 12-lead ECGs, and ophthalmic assessments. Tolerability will be assessed by the incidence of AEs leading to study drug interruption, dose reduction, or discontinuation.

10.5.1 Adverse Events

10.5.1.1 Definitions

An AE is defined as the appearance of (or worsening of any pre-existing) undesirable sign(s), symptom(s), or medical condition(s).

An SAE is defined as one of the following:

- Is fatal or life-threatening.
- Results in persistent or significant disability/incapacity.
- Constitutes a congenital anomaly/birth defect.
- Is medically significant, ie, defined as an event that jeopardizes the subject or may require medical or surgical intervention to prevent 1 of the outcomes listed above.
- Requires inpatient hospitalization or prolongation of existing hospitalization, unless hospitalization is for:
 - Routine treatment or monitoring of the studied indication, not associated with any deterioration in condition.
 - Elective or preplanned treatment for a pre-existing condition that is unrelated to the indication under study and has not worsened since signing the informed consent.

- Treatment on an emergency outpatient basis for an event not fulfilling any of the definitions of a SAE given above and not resulting in hospital admission.
- Social reasons and respite care in the absence of any deterioration in the subject's general condition.

In addition, any suspected transmission of an infectious agent via a medicinal product will be considered an SAE at study centers in the EU.

10.5.1.2 Clarifications for AE Definitions

Abnormal laboratory values or test results constitute AEs only if they induce clinical signs or symptoms, are considered clinically significant, require therapy (eg, hematologic abnormality that requires transfusion or hematological stem cell support), or require changes in study drug(s).

Recurrence or progression of underlying malignancy is not considered as an AE if it is clearly consistent with the suspected recurrence or progression of the underlying cancer as defined by RECIST criteria v1.1, or other criteria as determined by protocol. Hospitalization due solely to the recurrence or progression of underlying malignancy should NOT be reported as an SAE.

Clinical symptoms of recurrence or progression may be reported as AEs if the symptom cannot be determined as exclusively due to the recurrence or progression of the underlying malignancy, or does not fit the expected pattern of recurrence or progression for the disease under study.

Symptomatic deterioration may occur in some subjects. In this situation, recurrence or progression is evident in the subject's clinical symptoms, but is not supported by the tumor measurements. Or, the disease recurrence or progression is so evident that the investigator may elect not to perform further disease assessments. In such cases, the determination of clinical recurrence or progression is based on symptomatic deterioration. These determinations should be a rare exception as every effort should be made to document the objective recurrence or progression of underlying malignancy.

Overdose of study drug is to be reported as an AE when drug is administered or taken at a daily dose ≥ 200 mg and the overdose is associated with signs or symptoms potentially related to study drug (see also Section 10.5.1.5).

If there is any uncertainty about an AE being due to recurrence or progression of the disease under study, it should be reported as an AE or SAE.

10.5.1.3 Recording Adverse Events

After a subject signs the molecular prescreening ICF and/or the main study ICF and until a subject is randomly assigned to study treatment, AEs will only be captured if they meet the definition of serious and are reported to be causally related with study procedures (eg, an invasive procedure such as biopsy). Any other appearance of (or worsening of any pre-existing) undesirable sign(s), symptom(s), or medical condition(s) should be recorded as medical history.

Before randomization, any SAEs reported as causally related with study procedures will be captured on a paper SAE Report form. After randomization, all AEs and all SAEs will be captured and reported in the eCRF.

Conditions already present at the time of informed consent should be recorded in the Medical History eCRF.

AEs (including lab abnormalities that constitute AEs) should be described using a diagnosis whenever possible, rather than individual underlying signs and symptoms. When a clear diagnosis cannot be identified, each sign or symptom should be reported as a separate AE.

The following information is to be captured in the eCRF for each AE: severity grade (CTCAE version 5.0, Grade 1-5); duration (start and end date); relationship to study drug; action taken with respect to study drug; whether medication or therapy was given; outcome; and whether the event was serious and seriousness criteria.

AE monitoring should be done from the time of informed consent and continue through 30 days after the last dose of study drug.

10.5.1.4 Reporting Serious Adverse Events

Before randomization, any SAEs causally related with study procedures will be captured on a paper SAE Report Form and must be reported to Covance Safety immediately and under no circumstances later than 24 hours of learning of its occurrence via email: [contact]; or fax (please refer Study Manual for country-specific fax numbers).

After randomization, every SAE, regardless of suspected causality, occurring after the subject has been randomly assigned to study treatment through 30 days after the subject has taken his/her last dose of study drug must be reported on the SAE eCRF immediately and under no circumstances later than 24 hours of learning of its occurrence. If there are any issues with electronic data capture (EDC), please send a completed paper SAE report form to Covance Safety via email: [contact] or fax (please refer to the Study Manual for country-specific fax numbers). Any SAEs experienced after this 30-day period should only be reported to Covance Safety if the investigator suspects a causal relationship to the study drug.

Any additional information for the SAE including recurrent episodes, complications, or progression of the initial SAE must be reported as follow-up to the original episode within 24 hours of the investigator receiving the follow-up information. An SAE occurring at a different time interval or otherwise considered completely unrelated to a previously reported one should be reported separately as a new event.

Follow-up information is submitted in the same way as the initial SAE. Each reoccurrence, complication, or progression of the original event should be reported as a follow-up to that event regardless of when it occurs. The follow-up information should describe whether the event has resolved or continues, if and how it was treated, and whether the subject continued or withdrew from study participation.

If the SAE is not previously documented in the Investigator's Brochure or Package Insert (new occurrence) and is thought to be related to the study drug, a Covance Safety Associate may

urgently require further information from the investigator for Health Authority reporting. Covance Safety may need to issue an Investigator notification, to inform all Investigators involved in any study with the same drug that this SAE has been reported. Suspected Unexpected Serious Adverse Reactions will be collected and reported to the competent authorities and relevant ethics committees in accordance with Directive 2001/20/EC or according to national regulatory requirements in participating countries.

More detailed information on SAE Reporting can be found in the Study Manual.

10.5.1.5 Adverse Events of Special Interest

The following AEs, if otherwise not qualified as an SAE, are to be reported within 24 hours in the EDC system.

- Potential drug induced liver injury that meets the following criteria (elevation of bilirubin and ALT/AST that meet Hy's Law criteria [[FDA Guidance for Industry 2009](#)]):
 - Treatment-emergent ALT or AST $>3 \times$ baseline value in combination with total bilirubin $\geq 2 \times$ ULN (of which $\geq 35\%$ is direct bilirubin)
 - Treatment-emergent ALT or AST $>3 \times$ baseline value in combination with clinical jaundice.
- Retinal detachment of Grade 3 or higher, regardless of relationship to study drug.
- Keratitis Grade 3 or higher with suspected relationship to study drug.
- Pathological fractures, defined as fractures potentially related or related to metastatic tumor to bone and/or study drug.
- Vascular calcifications with accompanying ischemic AEs.
- Overdose, defined as a daily dose ≥ 200 mg of study drug, and that is associated with an AE that is potentially related to study drug.

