 - a. Absolute neutrophil count (ANC) $< 1,000/\text{mm}^3$ ($1.0 \times 10^9/\text{L}$).
 - b. Platelets $< 75,000/\text{mm}^3$ ($< 75 \times 10^9/\text{L}$).

- c. Hemoglobin <8.5 g/dL; transfusion support is allowed if >1 week before randomization and hemoglobin remains stable.
- 13. Have insufficient hepatic and renal function:
 - a. Total bilirubin $>1.5 \times$ upper limit of normal (ULN) of the testing laboratory (for subjects with documented Gilbert syndrome, direct bilirubin must be $\leq 1.5 \times$ ULN and enrollment requires approval by the medical monitor).
 - b. AST/SGOT and ALT/SGPT $>2.5 \times$ ULN of the testing laboratory.
 - c. Serum creatinine $>1.5 \times$ ULN or a calculated (using the Cockcroft-Gault [C-G] formula [[Cockcroft 1976](#)]) or measured creatinine clearance of <30 mL/min.
- 14. Have amylase or lipase $>2.0 \times$ ULN.
- 15. Have abnormal calcium or phosphorus:
 - a. Inorganic phosphorus higher than $1.02 \times$ ULN of the testing laboratory.
 - b. Total serum calcium (can be corrected) higher than $1.02 \times$ ULN of the testing laboratory.
- 16. Have clinically significant cardiac disease including any of the following:
 - a. New York Heart Association (NYHA) Class $\geq 2B$; subjects with known history or current symptoms of cardiac disease, or history of treatment with cardiotoxic agents, should have a clinical risk assessment of cardiac function using the NYHA classification.
 - b. Uncontrolled hypertension (refer to European Society of Cardiology and European Society of Hypertension guidelines [[Williams 2018](#)]).
 - c. Presence of CTCAE v5.0 Grade ≥ 2 ventricular arrhythmias, atrial fibrillation, bradycardia, or conduction abnormality.
 - d. Unstable angina pectoris or acute myocardial infarction ≤ 3 months before the first dose of study drug.
 - e. Average QTcF >470 msec (males and females). Note: If the QTcF is >470 msec in the first ECG, a total of 3 ECGs separated by ≥ 5 minutes should be performed. If the average of these 3 consecutive results for QTcF is ≤ 470 msec, the subject meets eligibility in this regard.
 - f. History of congenital long QT syndrome.
- 17. Have had a recent (≤ 3 months before the first dose of study drug) transient ischemic attack or stroke.

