7.2 Information on Dosing with Study Drug

7.2.1 *Subject Instructions for Dosing*

Subjects with mild or moderate renal impairment (creatinine clearance 30 mL/min to ≤ 89 mL/min) should be administered a starting dose of 100 mg QD infigratinib on a 3 week on (21 day)/1 week off (7 day) schedule. Subjects with mild (total bilirubin $>$ ULN to $1.5 \times$ ULN or AST $>$ ULN) and moderate hepatic impairment (total bilirubin $>$ 1.5 to $3 \times$ ULN with any AST) should be administered a starting dose of 100 and 75 mg QD of infigratinib, respectively, on a 3 weeks on (21 day)/1 week off (7 day) schedule. For subjects with combined hepatic and renal impairment, the lower of the 2 starting doses should be administered.

Subjects should be instructed to take the daily dose of study drug in the morning, at approximately the same time each day (24 \pm 4-hour interval). Subjects will take their first dose of study drug at the study center on Cycle 1 Day 1 (C1D1). On the days of PK sampling, subjects should not take their study drug dose at home; subjects should bring their study drug with them to the study center where dosing of study drug will be supervised and administration time recorded. Administration may fall outside of the \pm 4-hour interval on the days of PK sampling. On PK sampling days after C1D1, the time of the last study drug dose (ie, time of study drug administration on the previous day) before the predose PK sample will be recorded in the eCRF.

Study drug should be taken in the fasted state at least 1 hour before or 2 hours after a meal. It should be taken with a large glass of water (\sim 250 mL) and consumed over as short a time as possible. Subjects should be instructed to swallow the capsules whole and not chew them.

If the subject forgets to take the scheduled dose of study drug in the morning (other than on a day of PK sampling), he/she should not take the dose more than 4 hours after the usual time and should continue treatment the next day. Any such doses that are missed should be skipped altogether and should not be replaced or made up at the next scheduled dosing.

If vomiting occurs following dosing with study drug, re-dosing is not permitted the same day. Dosing should resume the next day. If vomiting occurs on a PK sampling day within the first

4 hours postdosing, this event is to be noted on the Dose Administration page of the eCRF, as well as on the AE page, as appropriate.

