Serum creatinine increase Grade ≥ 2	If serum creatinine CTCAE Grade ≥ 2 has been demonstrated in conjunction with hyperphosphatemia, serum creatinine levels must be repeated at least weekly until resolution. 24-hour urine collection should be obtained as clinically indicated for total phosphate, calcium, protein, and creatinine clearance. Ultrasound examination of the kidneys should be performed as indicated to evaluate de-novo calcifications until resolution or stabilization of creatinine.
Serum creatinine increase Grade ≥ 3 ($>3.0 \times$ ULN or $>3.0 \times$ baseline)	Discontinue study drug.
INVESTIGATIONS – HEPATIC	
Blood Bilirubin Increased (for subjects with Gilbert Syndrome, these dose modifications apply to changes in direct bilirubin only)	
Grade 2 (bilirubin $> 1.5 - 3.0 \times$ ULN if baseline was normal; $>1.5 - 3.0 \times$ baseline if baseline was abnormal)	Hold dose of study drug until resolved to CTCAE Grade ≤ 1 , then: 
• If resolved within ≤ 7 days, maintain dose level of study drug.• If not resolved within ≤ 7 days, \downarrow 1 dose level of study drug.
Grade ≥ 3 (bilirubin $>3.0 \times$ ULN if baseline was normal; $>3.0 \times$ baseline if baseline was abnormal)	Discontinue study drug. Note: If CTCAE Grade 3 or 4 hyperbilirubinemia is due to hemolysis, then \downarrow 1 dose level of study drug and continue treatment at the discretion of the investigator.
AST or ALT Increased	
Grade 3 ($>5.0 - 20.0 \times$ ULN if baseline was normal; $>5.0 - 20.0 \times$ baseline if baseline was abnormal)	Hold dose of study drug until resolved to CTCAE Grade ≤ 1 or baseline, then: 
• If resolved within ≤ 7 days, \downarrow 1 dose level of study drug.• If not resolved within ≤ 7 days, discontinue study drug.
Grade 4 ($>20.0 \times$ ULN if baseline was normal; $>20.0 \times$ baseline if baseline was abnormal)	Discontinue study drug.

Worst Toxicity CTCAE ^a (version 5.0) Grade (Unless Otherwise Specified)	Dose Modifications any Time During a Cycle of Therapy
AST or ALT and Bilirubin Increased	
AST or ALT >3.0 - 5.0 × ULN and total bilirubin >2.0 × ULN without liver metastasis or evidence of disease progression in the liver	Hold dose of study drug until both transaminases and bilirubin resolved to CTCAE Grade ≤ 1 or baseline, then: 
• If resolved within ≤ 7 days, \downarrow 1 dose level of study drug.• If not resolved within ≤ 7 days, discontinue study drug.

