AST or ALT >5.0 × ULN and total bilirubin >2.0 × ULN	Discontinue study drug
LABORATORY/METABOLIC DISORDERS	
Amylase and/or Lipase Increase	
General Comment:	A CT scan or other imaging study to assess the pancreas, liver, and gallbladder should be performed as clinically indicated within 1 week of the first occurrence of any CTCAE Grade ≥ 3 amylase and/or lipase.
Grade 3 (amylase or lipase >2.0 - 5.0 × ULN with signs or symptoms; >5.0 × ULN and asymptomatic)	Hold dose of study drug until resolved to CTCAE Grade ≤ 2 , then: 
• \downarrow 1 dose level of study drug.• If not resolved within ≤ 14 days, discontinue study drug. For recurrent Grade 3 asymptomatic lipase or amylase elevation despite dose reduction, study drug should be held and continuation of therapy should be discussed with the medical monitor following resolution to Grade ≤ 2 .
Grade 4 (amylase or lipase >5.0 × ULN and with signs or symptoms)	For any Grade 4 lipase or amylase elevation, study drug should be held and continuation of therapy should be discussed with the medical monitor following resolution to Grade ≤ 2 .
Hypophosphatemia	
Serum phosphate <LLN - 2.0 mg/dL (0.6 mmol/L)	Maintain dose level of study drug; decrease or hold dose of phosphate binder and optimize standard diet or medical therapy as clinically indicated to increase phosphate level.
Serum phosphate <2.0 - 1.0 mg/dL (<0.6 - 0.3 mmol/L)	Hold dose of study drug until resolved to >2.0 mg/dL (>0.6 mmol/L), then: 
• \downarrow 1 dose level of study drug.• If not resolved within ≤ 14 days, discontinue study drug.
Serum phosphate <1.0 mg/dL (<0.3 mmol/L) (life threatening consequences)	Discontinue study drug.
Hyperphosphatemia	
General Comment:	Optimize dose and schedule of phosphate lowering therapy in accordance with the package insert, or local or institutional guidelines.
Serum phosphate >5.5 - \leq 7.5 mg/dL	Maintain dose level of study drug and optimize phosphate-lowering therapy as clinically indicated.

Worst Toxicity CTCAE ^a (version 5.0) Grade (Unless Otherwise Specified)	Dose Modifications any Time During a Cycle of Therapy

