Subjects whose study drug is interrupted or permanently discontinued due to an AE or clinically significant laboratory value must be followed up at least once a week (or more frequently if required by institutional practices, or if clinically indicated) for 4 weeks, and subsequently at 4-week intervals, until resolution or stabilization of the event, whichever comes first. Clinical experts or specialists, such as an ophthalmologist, endocrinologist, dermatologist, should be consulted as deemed necessary. Further guidelines and dose modifications for the management of specific study drug-induced toxicities (hyperphosphatemia, diarrhea) are provided in [Table 6](#). All subjects must be followed up for AEs and SAEs for 30 days following last dose of study drug.

7.2.6 *Anticipated Risks and Safety Concerns for Infigratinib*

Eligibility criteria as well as specific dose modification and stopping rules are included in this protocol. Guidelines for prophylactic or supportive treatment for expected toxicities, including management of study drug-induced AEs (eg, hyperphosphatemia, renal toxicities) are provided in [Table 6](#) and Section [7.5](#). For more information, refer to the nonclinical toxicity and/or clinical data presented in the infigratinib Investigator's Brochure.

Treatment of AEs or lab abnormalities should follow the protocol where specified, otherwise local institutional guidelines with regard to safety management should apply.

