- Lost to follow-up (defined as no contact after 3 documented attempts by telephone followed by 1 attempt via letter [eg, certified mail, if available]).
- Subject request; if a subject withdraws consent from study treatment, it is required to document if the subject agrees or not 1) with continuation with study assessments; 2) to be followed for long-term follow-up and initiation of new anticancer therapies.
- Investigator request
- Use of other investigational therapies.

- Use of anticancer therapy (eg, chemotherapy, biologic or radiation therapy, surgery) other than the study drug. Exceptions are non-systemic treatments for low-grade or noninvasive UTUC or NMIBC, such as intravesical treatment, mitomycin gel, or BCG instillation.

The investigator must notify the sponsor/representatives if a subject is discontinued prematurely from study drug for any reasons, including reasons other than radiological or pathologic local/regional or contralateral invasive or metastatic recurrence. Subject's withdrawal from treatment must be documented and must also capture subject's permission or not to be followed for long-term follow up and anticancer therapy initiation. At the time of discontinuation of study drug, subjects are to complete the EOT visit (no later than 5 days after treatment discontinuation), the 30-day Follow-up visit (according to [Table 2](#) and Section [9.7](#)), and subsequent follow-up visits and assessments, according to [Table 2](#), Section [9.8](#), and Section [9.9](#).

The reason for treatment discontinuation is to be documented in the eCRF including identifying one reason as the primary reason for treatment discontinuation. The investigator should make every effort to determine why a subject is lost to follow-up or withdraws consent and record this information in the eCRF. Further, if a subject is discontinued from treatment due to protocol deviation or Investigator's request, specifics are to be recorded in the eCRF.

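### With baseline ALT or AST above ULN, a combined liver elevation for which Table 6 holds or stops drug can miss the 24-hour liver AESI (minor)

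*Protocol*

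**What the plan says.** **Expedited reporting (Protocol 10.5.1.5).** AESIs that do not already qualify as SAEs are reported within 24 hours. The liver entry has two limbs, and both are treatment-emergent. The first is ALT or AST above three times the "baseline value in combination with total bilirubin" of at least 2 × ULN, of which at least 35% is direct. The second is ALT or AST above three times the "baseline value in combination with clinical jaundice". The entry refers to Hy's Law, but the two limbs are the operative criteria and neither offers a ULN alternative.

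**Dosing (Protocol 7.2.5.1, Table 6, combined AST/ALT and bilirubin rows).** Drug is held for AST or ALT >3.0 to 5.0 × ULN with total bilirubin >2.0 × ULN, "without liver metastasis or evidence of disease progression in the liver". Drug is discontinued for "AST or ALT >5.0 × ULN and total bilirubin >2.0 × ULN", with no metastasis condition. Neither row adjusts for an abnormal baseline. The isolated AST/ALT row and the bilirubin row do. Table 6 as a whole covers AEs judged possibly related to study drug.

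**Who can enter with raised enzymes.** Exclusion 13b in Section 6.2 removes subjects with "AST/SGOT and ALT/SGPT $>2.5 \times$ ULN of the testing laboratory", so values above ULN and up to 2.5 × ULN are allowed. Section 7.2.1 foresees this group, although it names AST only: subjects with mild and moderate hepatic impairment, mild including AST above ULN, "should be administered a starting dose of 100 and 75 mg QD of infigratinib, respectively".

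**The concern.** The expedited-reporting rule scales with the subject's own baseline, while the combined dosing rule does not. For a subject who enters with raised enzymes, the reporting cut rises above the level at which the protocol itself interrupts or ends treatment. An event managed as a possibly drug-related liver problem, and serious enough to stop drug, can then fall outside the entry meant for possible drug-induced liver injury. The jaundice limb does not rescue it, because it carries the same enzyme multiple.

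What is at stake is the speed of notification. A combined enzyme and bilirubin rise is the pattern a sponsor most wants to hear about promptly, and Section 7.2.1 already lowers the starting dose for some of the subjects concerned.

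**Working it through.** There is no stated figure to reproduce; the check is a comparison of thresholds.

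**Inputs.** Let b be an enzyme's baseline in multiples of ULN, with b up to 2.5 (exclusion 13b).
- AESI enzyme condition (10.5.1.5): reading > 3 × b.
- Table 6 combined hold: reading >3.0 to 5.0. Combined stop: reading >5.0. Both need bilirubin >2.0 × ULN, which meets the AESI's ≥2 × ULN.

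**Formulas.**
- Hold readings missed: above 3.0, up to the smaller of 3b and 5.0. This range is non-empty when 3b > 3, that is b > 1.0.
- Stop readings missed: above 5.0, up to 3b. This range is non-empty when 3b > 5, that is b > 5/3 = 1.67.

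| Baseline b (× ULN) | AESI cut 3b (× ULN) | Hold readings missed | Stop readings missed |
|---|---|---|---|
| 0.8 | 2.4 | none | none |
| 1.0 | 3.0 | none | none |
| 1.2 | 3.6 | >3.0 to 3.6 | none |
| 1.5 | 4.5 | >3.0 to 4.5 | none |
| 1.67 | 5.0 | >3.0 to 5.0 (whole row) | none |
| 2.0 | 6.0 | whole row | >5.0 to 6.0 |
| 2.5 | 7.5 | whole row | >5.0 to 7.5 |

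These are ranges of laboratory values, not shares of patients.

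**Both enzymes matter.** The AESI says ALT or AST, so an event is missed only if each enzyme stays at or below three times its own baseline.
- *Stop example.* ALT 2.0 to 5.5 × ULN gives 5.5/2.0 = 2.75. AST 1.8 to 4.5 × ULN gives 4.5/1.8 = 2.50. With bilirubin 2.5 × ULN, 50% direct, the combined row stops drug. Neither AESI limb is met, with or without jaundice. The isolated AST/ALT row is not reached either: Grade 3 from an abnormal baseline starts above 5 × baseline, here 5 × 2.0 = 10.0 and 5 × 1.8 = 9.0 × ULN.
- *Hold example.* ALT 1.5 to 4.2 × ULN gives 2.80. AST 1.4 to 3.8 × ULN gives 2.71. With bilirubin >2.0 × ULN and no liver metastasis or progression, drug is held and neither limb is met.
- *One enzyme raised.* AST 2.0 to 5.5 × ULN gives 2.75. If baseline ALT is 0.9 × ULN, ALT must stay at or below 3 × 0.9 = 2.7 × ULN for the event to be missed.

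**Check of the remedy.** If the enzyme condition becomes > 3 × baseline or > 3 × ULN, the effective cut is the smaller of 3b and 3.0. Every combined-row reading exceeds 3.0, so the enzyme part is met at every baseline. For b ≤ 1.0 nothing changes.

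**The case against.** The strongest reply is that this is a deliberate design choice. One rule governs reporting and the other dosing, and nothing requires them to share thresholds. A baseline-relative rule fits the protocol's practice in the isolated AST/ALT and bilirubin rows. That explains the wording. It does not explain why the combined rows act at ULN multiples in these subjects while the prompt report does not follow.

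A second reply is that such an event would usually be an SAE. Section 10.5.1.1 counts medically significant events as serious, and Section 10.5.1.4 then requires a report within 24 hours. This stands as a real limit, especially with jaundice. It rests on investigator judgement, however: no text makes a combined elevation serious automatically.

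A third reply is that little is lost, and this also stands:
- Drug is held or stopped, and a combined-row hold not resolved within 7 days becomes a discontinuation.
- The laboratory change goes on the AE page (10.5.3).
- The subject "must be followed up at least once a week" for four weeks, then every four weeks until resolution or stabilization (7.2.5.2).
- "The investigator must notify the sponsor/representatives if a subject is discontinued prematurely from study drug for any reasons" (8.1.1), although no clock is stated.
- The data monitoring committee sees AE rates and discontinuations (10.5.9), and SAP 8.10.4 lists potential Hy's law cases.

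A reader might also infer that the protocol reports trivial rises and ignores serious ones, because ALT from 0.8 to 2.5 × ULN (2.5/0.8 = 3.125 × baseline) with bilirubin 2.5 × ULN, 50% direct, is an AESI while the stop example is not. The documents do not support that reading. With a normal baseline, bilirubin of 2.5 × ULN is itself a Grade 2 hold in Table 6, so the contrast case is not trivial.

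**Conclusion.** The gap is real and minor. For subjects entering with ALT or AST above ULN, a Table 6 combined hold (baseline above 1.0 × ULN) or stop (baseline above 1.67 × ULN) can fall outside both liver limbs if neither enzyme exceeds three times its own baseline. Only the guaranteed 24-hour report is lost, and only for events that the investigator judges possibly related (the condition in Table 6's title) and not serious.

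Two stronger inferences are not supported. Subjects are not left on drug, and liver data do not go uncollected; the provisions above show otherwise. Nor can the number of missed events be stated, because the documents give no count of subjects with raised baseline enzymes. SAP Section 1 says the study closed early for reasons unrelated to efficacy or safety, so the practical effect in this trial is small.

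The conclusion assumes that sites apply the two limbs as written and that 13b caps each enzyme at 2.5 × ULN. Read literally, its 'and' would let one enzyme exceed that at entry, which would widen the gap.

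**What to change.** In both liver limbs of Section 10.5.1.5, replace the enzyme condition with: *ALT or AST >3 × baseline value or >3 × ULN*. Keep the treatment-emergent qualifier, the bilirubin condition (≥2 × ULN, ≥35% direct) and the jaundice condition as they are.

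Do not define the AESI by reference to the Table 6 rows, and do not add a liver-metastasis exclusion. The stop row and the present limbs carry no such exclusion, so adding one would leave some stop events uncovered. A reference to Table 6 could also bring in its relatedness condition, which the AESI does not have.

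The cost is one phrase in each limb and a few more expedited reports. At the upper entry limit a rise of 3.0/2.5 = 1.2-fold would satisfy the enzyme part, but the bilirubin or jaundice condition must still be met. A combined elevation with less than 35% direct bilirubin and no jaundice would stay outside the AESI, as it does now at any baseline.
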